STUDY PROTOCOL: MOMSonLINE2

NCT#: NCT04600076

VERSION DATE: 18NOV2020

Study Protocol: MOMSonLINE2

Background

Stillbirth (death in the second half of pregnancy) and early infant death (in the first month of life) are devastating events for families. Bereaved mothers have significantly higher rates of depression, post-traumatic stress disorder, and generalized anxiety disorder. To date, there are very few bereavement interventions (only 2 identified in a recent systematic review) for parents after perinatal death.

Internet message boards and social media sites are common sources of support for women with pregnancy and infant loss. Research by the study team and others shows that users subjectively describe tremendous support from these sites and say they feel less alone in their grief. The boards allow users to post free of charge at any time of day or night and quickly get support from others. However, despite the proliferation of such groups for all sorts of health and social issues, there are very few evaluations of whether such existing groups can improve mental health outcomes, sense of belonging and support, and reduce grief. Virtually all studies of internet support involve the development of a brand new intervention and/or brand new on-line group, despite the fact that millions of users are already connected with existing groups.

We recently completed a 6-week pilot study (MOMSonLINE) which randomized 30 women with remote history of perinatal loss (6-7 years previously) to one of three study arms: a closed Facebook group for perinatal loss, an anonymous BabyCenter group for perinatal loss, or a control arm without an interactive support component. We collected data from monitoring site usage, online and text surveys, and semi-structured interviews. Mothers reported clear preference for the BabyCenter site and the study allowed us to test various aspects of the study including text messaging, on-line enrollment and consent, and implementation. We also identified important challenges with recruitment and retention, including low enrollment of women of color and difficulty with trying to hand-track usage of the sites.

BabyCenter LLC is a member of the Johnson & Johnson family of companies and provides global digital parenting content. The company estimates that 7 in 10 expectant moms in the United States use BabyCenter.com. Company products include websites, mobile apps, online communities, email series, social programs, and public health initiatives. We propose to use one of the online communities in this study: "Miscarriage, Stillbirth, & Infant Loss Support." <https://community.babycenter.com/groups/a15155>.

Proposed Study and Aims

We now are proposing a new pilot study (MOMSonLINE2) to evaluate recruitment specifically for women of color who are closer to the time of perinatal loss. This is a feasibility study. We will track data about group usage through a new collaboration with BabyCenter.com. Once this pilot is completed, we will have adequate data and knowledge to develop a much larger randomized control study of on-line support outcomes after perinatal loss.

Aim #1: Demonstrate the ability to recruit and retain recently-bereaved women of color to the pilot through a partnership with the Michigan Department of Health and Human Services.

Aim #2: Test a collaboration with BabyCenter which would provide proprietary data about the support group usage of our study participants and allow much more accurate tracking of use.

[figure not shown]
Aim #3: To test whether incentives based on group usage (compared with incentives based on survey completion) lead to increased engagement with the online group.

Aim #4: To test preliminary mental health outcomes (symptoms of depression, anxiety, post-traumatic stress, and grief) with a pilot group using standardized measures.

Research Methods

Recruitment: From 2011-2013 we conducted the Michigan Mothers Study, a collaboration with the Michigan Department of Health and Human Services (MDHHS) for a population-based statewide survey of mental and physical health outcomes of mothers with stillbirth, early infant death, or live birth. At the time, birth and death certificates in Michigan were submitted in writing by hospital staff and it took 6-8 months after delivery for the state to identify bereaved and live-birth parents. In the intervening years, MDHHS has transitioned to on-line reporting of vital records so birth and death information is now available to the state within days, rather than months. Our prior work has shown that women want information about online support within the first month after loss so this change in reporting will allow us to reach out much earlier.

In our Michigan Mothers Study, we were able to protect the confidentiality of non-participants by having MDHHS keep the identity of parents. MDHHS mailed out our first surveys, and parents who wanted to participate completed and returned the survey with their identifying data. Those who did not want to be included could ignore the mailing or return a card with random study ID declining to participate. In this way, only MDHHS knew personal information about non-participants. For this study, MDHHS will send our first mailing (a bereavement card expressing consolation for the loss and mentioning the study and that we will contact them in a few weeks). The bereavement card will go out no earlier than 3 weeks after the loss of their baby. Subsequent mailings will have information describing the study and how to enroll.

[figure not shown]

Subjects and Sample Size

This study will only enroll non-Caucasian women. African-American women face twice the risk of perinatal death compared to white women. They have similar rates of depression and post-traumatic stress disorder after a loss but are far less likely to seek mental health care. In previous research, bereaved African-American mothers expressed strong interest in on-line support but most were unaware this existed at the time their baby died. For this pilot MDHHS will send mailings to 200 recently bereaved non-Caucasian mothers. Assuming a 20% response rate, this will enroll 40 women in the study. We are requesting approval for up to 75 mothers in case more women respond than we anticipate. (We had a 22% participation rate among this group in the Michigan Mothers Study). MDHHS will send the initial condolence card no earlier than 3-weeks or later than 8-months post-loss.

Inclusion criteria: Michigan residence and delivery; age 18 or older at delivery; non-Caucasian race and/or Hispanic ethnicity; read/speak English; gave birth to a stillborn baby or had an infant death in the first 28 days of life; did not give the baby up for adoption pre-loss; and internet access.

Mailings: MDHHS will send the initial condolence card followed by up to three survey invitations and a reminder post-card per Dillman protocol. The mailings will include a cover letter from MDHHS. The three invitations will also include a pre-stamped card which subjects may send back to the study team if they do not want to participate. The card contains only a random study ID. The study team will report this ID to MDHHS who will then remove the subject from their subsequent mailing lists.

Consent: Study invitations will describe the study and provide mothers with an online link to learn more about the study, email (or call) the study team with questions, answer eligibility screening questions, and to complete the full written consent on-line. This is a single-arm study to test recruitment and engagement.

Subjects will sign up for a BabyCenter account (unless they already have one), will agree to follow all the rules of the BabyCenter site and the community group, and agree to share their username with both the study team and with BabyCenter (so that BabyCenter can send us information about usage). As BabyCenter is a commercial web site, they have their own privacy rules and disclosure about what information they collect and/or share for users, described here: <https://www.babycenter.com/help-privacy>. BabyCenter automatically sends out a “daily digest” email with links to any new posts in the group which encourages members of a community support group to visit the group, and subjects in our study will get this same digest.

Participation: During the study, subjects will be asked to

- a. Sign on to the BabyCenter community group for people with pregnancy or infant loss at least 3x weekly for 6 weeks. Participants may choose to post or comment on the site but are not required to do so.
- b. Complete two on-line surveys (at the beginning and end of the study) which ask about demographics, use of social media, other types of support after the loss of their infant, satisfaction and experience with the on-line group. Both surveys will include 4 standardized instruments to measure depression (PHQ-8), anxiety (GAD-7), post-traumatic stress (PTSD-Checklist, civilian version), and grief (Perinatal Grief Scale).
- c. Receive 3 weekly text-messages from the study team (to remind them to go online to the group). BabyCenter staff can track usage patterns of participants who visit the group and are logged in. If a subject has not signed on for 4 days, information will be provided to alert the study team. We will then reach out to her by personalized text message or phone call to encourage participation and assess for barriers.
- d. Get two phone calls from the study team. The first will be made after they consent to ensure they understand the study and/or answer any questions. The second will be made in the middle of the study to assess for any problems signing on.
- e. Participate in a 10-20 minute semi-structured phone interview at the end of the 6-week study.

Tracking Usage: BabyCenter.com has agreed to share data about use of the pregnancy/infant support group among our study subjects. We will ask subjects to stay logged in when using the BabyCenter application, or bookmark the site in their browser, and mark the box “keep me logged in.” By marking this box, they will only be logged out if they purposefully log out, change browser, or clear their cookies. BabyCenter will provide the following information for each of our participants: the day and number of visits, page views, URLs visited in the group, and data on posts, comments, and “hugs” (similar to a “like” on Facebook). At the end of the study, BabyCenter will give us aggregate, de-identified data about activity of the full group, e.g. total number of weekly users, number of weekly posts, comments, and hugs.

[figure not shown]
Risks and benefits: The study is no more than minimal risk. We are asking bereaved mothers to go to an anonymous, public online support site. They are not required to post. Several experienced group members serve as volunteer group moderators. Extensive research by our team has shown that women typically find forums for loss to be supportive and help reduce the isolation which is very common in the months after a loss. There are no direct benefits to participants, but we are hopeful that by participating, some mothers may receive support and find satisfaction from supporting others.

Incentives

One study aim is to test how incentivizing different activities impacts participation. We will randomize participants either to a group which

- a) incentivizes support group participation (\$5 per week that they go to the BabyCenter.com group at least three times and \$20 for completion of the phone interview); or
- b) incentivizes survey completion (\$10 per survey and \$30 for completion of the phone interview).

Participants in either group can earn up to \$50—they are simply compensated for different parts of the study. Subjects may withdraw at any time and will be paid for all elements they have completed at the time of withdrawal. The incentives will help to cover if participants are charged by their internet provider for text messaging.

Online Safety:

BabyCenter has a site-wide process which allows any user to report on a post or comment they are concerned about, documented here: <https://www.babycenter.com/community-help-howto>. At the top of the loss group, there is a post which includes lists of other related support groups for loss as well as support sites outside of BabyCenter.com. Every posting and comment has the option to click a link to “Report this comment” where users can send a report to staff, to the group owners, or both. Users can also email the URL and text to [contact]. BabyCenter maintains a list of resources which include links to two national suicide hotlines: <https://www.babycenter.com/community-help-resources#articlesection16>. BabyCenter also has a section of resources at <https://www.babycenter.com/community-help-resources#articlesection1> which includes this statement:

Emergency

If you believe another person is a threat to himself, herself, or someone else, please call 911, your local police department, or any other appropriate government agency. Law enforcement officials can get help and get involved where BabyCenter cannot. However, we will cooperate with officials who contact us about any situation. They can reach us by emailing [contact].

In our surveys, we are using the PHQ-8 so will not be asking about suicidal thoughts. Nevertheless, we will include information about a toll-free 24-hour suicide hotline as a resource; the number will be placed in the survey, after the PHQ-8.

Analysis:

This single-arm feasibility study will primarily be descriptive and provide summary-type information. While we will assess mental health and grief outcomes, we recognize it is not powered for significance. It is meant to demonstrate ability to recruit, retain, and engage users and will also give preliminary data on our primary outcomes, including willingness of participants

to complete the measures. For the qualitative data, we will explore participant attitudes about online privacy and data monitoring, the experience online, and identify potential problems that may occur during recruitment in a larger trial. Qualitative interviews will be transcribed verbatim. Two researchers will review the transcripts to develop a preliminary codebook, code a subset of the interviews, and use an iterative process to revise the codebook. Transcripts will be re-coded and we will test inter-coder agreement using the final codebook. Transcripts will then be analyzed to identify themes emerging from the transcripts with particular focus on information to help us edit, adjust, or improve the intervention for the RCT.

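### Does using non-Caucasian in the mailing and enrolment sentences, but adding Hispanic ethnicity in the inclusion criteria, undermine the recruitment rate?

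*Combined protocol and SAP*

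**What the plan says.** Three statements in the section Subjects and Sample Size bear on the point.

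- Enrolment: "This study will only enroll non-Caucasian women".
- Mailing: "For this pilot MDHHS will send mailings to 200 recently bereaved non-Caucasian mothers". The next sentence gives the yield: "Assuming a 20% response rate, this will enroll 40 women in the study". In support, the protocol adds: "We had a 22% participation rate among this group in the Michigan Mothers Study".
- Eligibility: the inclusion criteria list "non-Caucasian race and/or Hispanic ethnicity", along with residence, age, language, type of loss, adoption and internet access.

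Under Consent, invited mothers follow an online link to "answer eligibility screening questions, and to complete the full written consent on-line". Aim #1, under Proposed Study and Aims, uses a broader label: "Demonstrate the ability to recruit and retain recently-bereaved women of color to the pilot". The text available does not give the query by which the state health department (MDHHS) selects its mailing list, and it does not define non-Caucasian.

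**The concern.** The and/or in the inclusion criterion makes Hispanic ethnicity sufficient by itself. A mother who is white and Hispanic therefore qualifies under the criteria but falls outside the literal mailing and enrolment sentences. Aim #1 adds a third, undefined label, and the 22% from the previous survey belongs to a group whose treatment of white Hispanic mothers is not stated.

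Recruitment is the first aim, and the enrolled-per-mailed rate is what a larger trial would plan from. MDHHS chooses whom to mail, and a separate online screen decides who may enrol. If the two worked from different definitions, either eligible mothers would go uninvited or some mothers would be invited and then refused. In the second case the observed rate would understate willingness to take part.

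**Working it through.** **Inputs from Subjects and Sample Size:** 200 mailed; 20% assumed response; 40 expected; 22% participation in the previous survey; approval sought for up to 75.

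**The plan's own figure.** 200 × 0.20 = 40, as stated. At the previous survey's rate, 200 × 0.22 = 44, so the 40 comes from the 20% and not from the 22%. The cap would be reached only at 75/200 = 37.5%. The exact (Clopper-Pearson) 95% interval for 40/200 is 14.7% to 26.2%.

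**Which statements disagree.** The enrolment and mailing sentences use the same term, and the 20% is applied to those same 200 mothers. These three agree with one another. Only the inclusion criterion is wider.

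**What that does to the rate.** The documents do not give the white Hispanic share of mothers meeting the criterion. Call it h, and assume 5%, 10% and 20%.

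1. *Shorthand reading* (non-Caucasian stands for the full criterion in all three places): the effect is nil.
2. *Literal mailing list.* Every mother mailed satisfies the race and ethnicity criterion, and nobody outside the list is invited. The rate has numerator and denominator from one population. Coverage is narrower: eligible mothers not mailed, per 200 mailed, number 200 × h/(1 − h).
3. *List built on the criterion, enrolment held to the literal sentence.* Mailed but unable to enrol: 200 × h. Enrolled: 0.20 × 200 × (1 − h).

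| Assumed h | Unmailed per 200 mailed (reading 2) | Mailed, cannot enrol (reading 3) | Enrolled (reading 3) | Apparent rate (reading 3) |
|---|---|---|---|---|
| 5% | 10.5 | 10 | 38 | 19% |
| 10% | 22.2 | 20 | 36 | 18% |
| 20% | 50.0 | 40 | 32 | 16% |

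Reading 3 shifts the rate by 1 to 4 percentage points, and all three values lie inside 14.7% to 26.2%.

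4. *List and enrolment both on the criterion, 200 mailed.* Take h = 20%, 20% response among the other mothers, and an assumed 10% to 30% among white Hispanic mothers. Enrolment is 200 × (0.8 × 0.20 + 0.2 × 0.10) = 36 at the low end and 200 × (0.8 × 0.20 + 0.2 × 0.30) = 44 at the high end.
5. *White Hispanic mothers mailed on top of the 200*, under the same assumptions: 40 + 50 × 0.10 = 45 to 40 + 50 × 0.30 = 55.

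Across all readings enrolment runs from 32 to 55, below the cap of 75.

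**How plausible reading 3 is.** It requires one word to include white Hispanic mothers in the mailing sentence and to exclude them in the enrolment sentence a few lines earlier. It also requires the online screen to follow the narrative sentence and not the listed criteria. The protocol gives no wording for the screening questions, so nothing in the text supports that.

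**The case for a change.** The best case for a change is that two parties apply the definition separately and the error would be hard to see. MDHHS alone holds the identities of mothers who do not take part, so the study team could not easily tell afterwards whom the list had missed. Mailings cannot be recalled, a single wording would cost almost nothing, and Aim #1 concerns precisely this population. Nor can a reader tell whether the 22% and the future observed rate describe the same women.

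Part of this stands. The sentences do differ, nothing in the text reconciles them, and on the literal reading white Hispanic mothers would be eligible but not invited. That is a question of coverage. It does not make the rate uninterpretable, because enrolled over mailed remains well defined for the mothers mailed. Nor does the rate depend on mailed and eligible mothers coinciding exactly: the criteria also require English, internet access and no adoption before the loss, none of which the mailing sentence mentions, so the two groups would differ even with race and ethnicity worded identically.

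The Aim #1 label does not compete with the criterion. The criterion reads as its working definition, which favours the shorthand reading. The composition of the group behind the 22% is a missing detail about a previous study, and the planned 40 does not rest on it.

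**Conclusion.** This is a loose piece of wording, and no change to the plan follows. An itemised inclusion criterion ordinarily governs over a narrative summary, and staff building the list or the screen would sensibly work from it; the effect is then nil. If the mailing sentence is followed literally, fewer eligible mothers are reached, but the rate keeps a clean denominator. Only the strained third reading moves the rate, by 1 to 4 points under assumed shares that no document supplies, and that lies within the sampling error of 40/200.

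The study is described under Analysis as mainly descriptive and not powered for significance, so no test or sample-size calculation depends on the definition. The planned 40, the 200 mailings and the cap of 75 all stand. Using the criterion's words throughout would be tidier, but it would change no result or conclusion.

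The conclusion rests on two assumptions: that mailed invitations are the only way in, as the protocol describes, and that the online screen applies the listed criteria.

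### The minimal-risk statement considers only the loss forum, although every woman needs an account on a general parenting site and the visible protocol has no step to limit exposure to pregnancy or baby content

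*Combined protocol and SAP*

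**What the plan says.** **The account.** The Consent text states: "Subjects will sign up for a BabyCenter account (unless they already have one", with the exception covering women who already hold one. It adds: "As BabyCenter is a commercial web site, they have their own privacy rules and disclosure".

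**The host.** Background says that the company "provides global digital parenting content". It lists the products: "Company products include websites, mobile apps, online communities, email series, social programs, and public health initiatives". It also reports an audience figure: "The company estimates that 7 in 10 expectant moms in the United States use BabyCenter.com". The web address of the loss group itself is given there.

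**How women are asked to use it.** Participation asks for at least three sign-ons a week to the loss group over six weeks. There are three reminder texts a week, and the team makes contact after four days without a sign-on. Of the two phone calls, one follows consent and deals with understanding and questions. The other comes mid-study and deals with sign-on problems. Tracking Usage asks women to remain logged in on the application, or to bookmark the site and tick the box that keeps the login active.

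**Risk and safety.** Risks and benefits rates the study as minimal risk and describes the exposure in this way: "We are asking bereaved mothers to go to an anonymous, public online support site". Its support is the team's research on loss forums. Online Safety describes site-wide reporting of posts and comments, resource lists, suicide hotlines and an emergency statement.

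**The concern.** The risk statement assesses one community group. What participants have to hold is an account with the company that hosts it, and that company's stated business is parenting content. Its stated audience includes expectant mothers. A woman who lost a baby recently could be shown or sent pregnancy or newborn material through the account that the study requires, and the risk paragraph does not consider this.

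Two things are at stake. The first is avoidable distress in women whose depression, anxiety, post-traumatic stress and grief the study measures. The second is the reading of engagement, a main feasibility question. A woman who stays away because of other content on the site may look, in the usage data, much like one with no interest in the loss group. The web addresses that BabyCenter is to report are those visited within the group.

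**Working it through.** This is mainly a comparison of sections. The little arithmetic involved shows scale and does not carry the argument.

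**Plan's own figure.** Subjects and Sample Size gives 200 mailings and an assumed 20% response: 200 × 0.20 = 40 women, as stated. Approval is sought for up to 75.

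**Requested use.** Participation: 3 sign-ons per week × 6 weeks = at least 18 sign-ons per woman. In one of the two incentive groups, each week with three visits is also paid.

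**Time since loss.** The condolence card goes out between 3 weeks and 8 months after the loss, and the invitations follow it. The earlier pilot, in which mothers preferred BabyCenter, enrolled women 6–7 years after their loss. Its experience says little about women whose pregnancy was recent.

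**Sections side by side.**

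- *What is required:* an account with the company, new or existing (Consent).
- *What the company offers:* parenting content, apps and email series, beyond the loss group (Background).
- *Where women are directed:* the reminders and the digest point to the loss group. The bookmark instruction names the site, although the group's own address is available in Background.
- *What the risk rating rests on:* evidence about loss forums only (Risks and benefits).
- *What the safety text covers:* concerning posts and crises. Ordinary pregnancy or baby content, and emails tied to an account, are not mentioned (Online Safety).
- *What the calls cover:* understanding, questions and sign-on problems. Account or email settings are not listed (Participation).

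**Result.** No section of the visible protocol checks account settings, limits other emails, warns participants, or makes the group page the point of entry. The nearest elements are the group digest and the bookmark. The digest is described as encouraging visits and the bookmark as supporting tracking, and neither is set up to limit exposure.

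**The case against.** The strongest reply is that the study asks women to visit only the loss group. The texts and the digest lead there, and any email series attached to an existing account would arrive whether or not the woman enrolled. The first call is open to questions. The four-day contact looks for barriers, and the end survey and interview ask about experience. A content problem therefore has several routes to come to light, and finding such problems is one purpose of a pilot. The consent pages were removed, so a warning may exist there.

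Much of this stands. It is why non-use caused by other content cannot be said to pass simply as low engagement. But the four-day contact, survey and interview act only after exposure, and none of the listed steps reduces it.

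A reader might also infer more than the documents support:

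- *That many women would use an account opened in the lost pregnancy.* Applying 7 in 10 to the sample gives 0.7 × 40 = 28 women, or 0.7 × 75 = 52.5, about 53. But the figure is the company's estimate of site use among US expectant mothers. It does not measure account holding in this population, and it does not say in which pregnancy an account was opened.
- *That women must stay logged in.* They are asked to. Only the account is required.
- *That women are told to keep an old account.* Holders are merely excused from signing up.
- *That both calls come early.* The second is mid-study.

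**Conclusion.** The point holds as a gap in the protocol text with a cheap remedy. The risk rating considers the loss forum alone, an account on a wider parenting site is compulsory, and no visible step limits what that account may show or send.

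Its size is unknown. The documents give neither the share of women with existing accounts nor any description of account settings, default emails or page layout. That participants would meet pregnancy or baby content is a reasonable inference from Background, but it is not stated. The finding is confined to the visible protocol, because the consent pages could contain a warning or guidance.

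No sample size, estimate or analysis changes. The case for acting rests on how recent these losses are and how little the change costs. It does not rest on a demonstrated frequency of harm.

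**What to change.** 1. In Tracking Usage, have women bookmark the loss group's own page, using the address in Background, instead of the site in general.
2. In the call already planned after consent, help each woman review her BabyCenter email and notification settings. Where the site allows, turn off those other than the loss-group digest.
3. Record for each participant that this was done.
4. Name exposure to pregnancy and baby content outside the group under Risks and benefits.

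Do not advise opening a second account. Usage is tracked through the username shared with BabyCenter while the woman is logged in. Visits made under an old account could be missed, which would work against Aim #2.

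The cost is a few minutes in an existing call, a changed bookmark instruction and a sentence under Risks. The limitation is that step 2 depends on site settings that the documents do not describe, so the team should confirm with BabyCenter that the group digest can be kept while other messages are switched off.

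### Is the Aim 3 comparison of incentive groups distorted because BabyCenter records only logged-in use and only one group is paid for visits?

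*Combined protocol and SAP*

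**What the plan says.** The relevant text is spread over several sections of the protocol.

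- **Proposed Study and Aims.** Aim 3 is "To test whether incentives based on group usage (compared with incentives based on survey completion) lead to increased engagement with the online group". Aim 2 tests a collaboration with BabyCenter that "would provide proprietary data about the support group usage of our study participants and allow much more accurate tracking of use".
- **Participation, item a.** Every participant is asked to "Sign on to the BabyCenter community group for people with pregnancy or infant loss at least 3x weekly for 6 weeks". Active contribution is optional: "Participants may choose to post or comment on the site but are not required to do so".
- **Participation, item c.** The log covers logged-in use: "BabyCenter staff can track usage patterns of participants who visit the group and are logged in". Inactivity triggers contact: "If a subject has not signed on for 4 days, information will be provided to alert the study team", followed by "We will then reach out to her by personalized text message or phone call to encourage participation and assess for barriers".
- **Participation, item d.** Of the two phone calls, "The second will be made in the middle of the study to assess for any problems signing on".
- **Tracking Usage.** All participants are asked to remain logged in. Once the relevant box is ticked, a session ends only through deliberate log-out, a different browser or cleared cookies. BabyCenter supplies visits by day, page views, URLs, posts, comments and hugs for each participant.
- **Incentives.** Participants are randomised. Group (a) earns $5 for each week with at least three visits and $20 for the interview. Group (b) earns $10 per survey and $30 for the interview.
- **Analysis.** The study is described as primarily descriptive and not powered for significance. No formal test is specified for Aim 3.

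**The concern.** Randomisation balances the women; it does not protect against an outcome that is recorded more completely in one group than in the other. Here the outcome comes from a log that depends on being logged in, and the intervention gives one group a possible financial reason to be logged. The site is described as public, so a woman might read posts without logging in. If group (b) did this more often, the log would understate its use, and group (a) would appear more engaged even with identical behaviour.

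The protocol describes no count of logged-out visits, overall or by group. The other usage variables do not fill the gap: visit-days and page views come from the same log, and posts, comments and hugs miss women who only read. At stake would be the reading of Aim 3 and, less directly, the completeness of the tracking that Aim 2 examines, both of which are meant to inform a larger trial.

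**Working it through.** **1. Payments (Incentives).** Group (a): 5 × 6 + 20 = $50. Group (b): 10 × 2 + 30 = $50. Both reproduce the stated maximum of $50. Visit-linked pay is 30/50 = 60% in group (a) and 0 in group (b), so the asymmetry in motive is real.

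**2. What bias would require.** Three links must all hold:

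| Link | Support in the protocol |
|---|---|
| The group can be read while logged out | Suggested by the description of the site as public; not stated |
| Paid weeks are verified from BabyCenter's log | Not stated |
| Group (b) is logged in less often than group (a) | None; inferred from motive only |

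The third link carries the bias. Incomplete recording that is equal in both groups creates no spurious difference when true use is equal.

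**3. Size if all three held.** The protocol gives no logged-in shares, so every share below is an assumption. With equal true use in both groups, taken as 3 visits per week (the requested minimum):

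spurious gap in mean weekly visits = 3 × (share in a − share in b)

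| Share a | Share b | Gap (visits per week) |
|---|---|---|
| 90% | 90% | 0 |
| 98% | 90% | 0.24 |
| 95% | 80% | 0.45 |
| 95% | 70% | 0.75 |
| 80% | 95% | −0.45 |

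**4. Scale against the pilot's precision.** Expected enrolment is 200 × 0.20 = 40, as stated in Subjects and Sample Size. The allocation ratio is not given; I assume 20 per group. With Poisson weekly counts of mean 3 within a woman and 6 weeks each, the variance of a woman's weekly mean is 3/6 plus the between-woman variance SD², so

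95% half-width = 1.96 × √[2 × (3/6 + SD²)/20]

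- SD 0: 1.96 × √0.05 = 0.44
- SD 1: 1.96 × √0.15 = 0.76
- SD 1.5: 1.96 × √0.275 = 1.03

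Every gap in the table lies inside the half-width at SD 1 (0.75 only just) and at SD 1.5. At SD 0, which assumes that all women visit at the same underlying rate, 0.45 and 0.75 exceed it.

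**5. How far the safeguards reach.** I simulated 42 days, with an alert after 4 consecutive days without a recorded visit. The share of women with at least one alert is:

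| Visit pattern | Fully recorded | 80% recorded |
|---|---|---|
| Exactly 3 days a week | 79% | 98% |
| Exactly 4 days a week | 17% | 78% |
| Exactly 5 days a week | 1% | 42% |
| Poisson, mean 3 a week | 98% | 99.6% |

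The alert is not specific: it also reaches fully recorded women and so cannot measure logged-out use. But at 80% recording it would reach 42% to 99.6% of women, whatever their payment group, and lead to a contact about barriers. The gaps in step 3 hold the shares fixed for six weeks and allow no effect of that contact. The simulation also drops visits independently, whereas a new browser or cleared cookies would tend to give a run of unrecorded visits, which is more likely to trip a 4-day alert.

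**The case for a change.** The strongest case for the concern is that none of the safeguards measures completeness. If capture did differ by group, the data described could not reveal it, and a bias does not shrink because the confidence interval is wide. The larger trial would inherit the problem, and a question about logged-out visits in contacts already planned would cost little.

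Part of this stands. No measure of logged-out use is described, and the precision comparison shows only that the illustrated gaps would rarely drive a conclusion in this pilot, not that bias is absent.

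It does not make the plan wrong. The behaviour requested of everyone is signing on, so a log of signed-on use measures what was asked. That argument is not decisive, because the payment rule speaks of going to the group and engagement is not defined.

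Nor is the added question clearly a better method. Recalled logged-out visits are imprecise: if both groups reported only half of them, at 95% versus 80% the remaining gap would be 3 × (0.975 − 0.900) = 0.225 visits per week, half of 0.45. Over-reporting could itself differ by group, since only one is paid for visits. Asking mid-study may change log-in behaviour, and the final interview is paid $20 in one group and $30 in the other, so response may differ too. The surveys and interview guide are not shown and may already cover the point.

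**Conclusion.** The concern does not hold. No figure, rule or analysis in the protocol is shown to be wrong. A bias in Aim 3 depends on the survey-incentive group being logged in less often, which rests on motive alone; depending on the assumed shares, the spurious gap is zero, positive (0.24 to 0.75 visits per week) or negative (−0.45). The sign-on request, the stay-logged-in request, the inactivity alert and the mid-study call apply to both groups, and the contrast belongs to a primarily descriptive pilot. The comparison of recorded, logged-in engagement can therefore stand as planned. Asking about logged-out visits is a matter of preference.

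This conclusion assumes that the safeguards are carried out alike in both groups and that results are read as recorded engagement. The sizes assume 3 true visits per week, 20 women per group and the logged-in shares shown. Evidence of a marked difference in logged-in shares between the groups would change the assessment.
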